8 STUDY ASSESSMENTS AND PROCEDURES

8.1 EFFICACY ASSESSMENTS

All outcome variables will be evaluated according to internationally accepted standards and scoring systems if available, i.e. the consensus definitions for pancreatic fistula of the International Study Group of Pancreatic Surgery (ISGPS).

The efficacy of the shark mouth modified pancreaticojejunostomy will be comprehensively assessed by the symptoms (e.g. febrile, abdominal pain, exsufflation), signs (e.g. tenderness, rebound tenderness, increased amount of drainage fluids), laboratory examinations of the blood (e.g. amylase), drainage fluids (e.g. amylase), and imaging examinations (e.g., abdominal CT scanning).

8.2 SAFETY AND OTHER ASSESSMENTS

The safety of the shark mouth modified pancreaticojejunostomy will be comprehensively assessed by the following:

- the vital signs (e.g. temperature, heart rate, respiratory rate and blood pressure),
- laboratory examinations of the blood (e.g. blood routine test, liver function).

8.3 ADVERSE EVENTS AND SERIOUS ADVERSE EVENTS

8.3.1 DEFINITION OF ADVERSE EVENTS (AE)

Adverse event means any untoward medical occurrence associated with the shark mouth modified pancreaticojejunostomy, whether or not considered intervention-related.

8.3.2 DEFINITION OF SERIOUS ADVERSE EVENTS (SAE)

An adverse event (AE) or suspected adverse reaction is considered "serious" if, in the view of either the investigator or sponsor, it results in any of the following outcomes: death, a life-threatening adverse event, inpatient hospitalization or prolongation of existing hospitalization, a persistent or significant incapacity or substantial disruption of the ability to conduct normal life functions, or a congenital anomaly/birth defect. Important medical events that may not result in death, be life-threatening, or require hospitalization may be considered serious when, based upon appropriate medical judgment, they may jeopardize the participant and may require medical or surgical intervention to prevent one of the outcomes listed in this definition.

8.3.3 CLASSIFICATION OF AN ADVERSE EVENT

8.3.3.1 SEVERITY OF EVENT

For adverse events (AEs) not included in the protocol defined grading system, the following guidelines will be used to describe severity.

- **Mild** – Events require minimal or no treatment and do not interfere with the participant's daily activities.
- **Moderate** – Events result in a low level of inconvenience or concern with the therapeutic measures. Moderate events may cause some interference with functioning.
- **Severe** – Events interrupt a participant's usual daily activity and may require systemic drug therapy or other treatment. Severe events are usually potentially life-threatening or incapacitating. Of note, the term "severe" does not necessarily equate to "serious".

8.3.3.2 RELATIONSHIP TO STUDY INTERVENTION

All adverse events (AEs) must have their relationship to study intervention assessed by the clinician who examines and evaluates the participant based on temporal relationship and his/her clinical judgment. The degree of certainty about causality will be graded using the categories below. In a clinical trial, the study product must always be suspect.

- **Related** – The AE is known to occur with the study intervention, there is a reasonable possibility that the study intervention caused the AE, or there is a temporal relationship between the study intervention and event. Reasonable possibility means that there is evidence to suggest a causal relationship between the study intervention and the AE.
- **Not Related** – There is not a reasonable possibility that the administration of the study intervention caused the event, there is no temporal relationship between the study intervention and event onset, or an alternate etiology has been established.

8.3.3.3 EXPECTEDNESS

The study monitor from the Ethics Committee of Peking University Third Hospital will be responsible for determining whether an adverse event (AE) is expected or unexpected. An AE will be considered unexpected if the nature, severity, or frequency of the event is not consistent with the risk information previously described for the study intervention.

8.3.4 TIME PERIOD AND FREQUENCY FOR EVENT ASSESSMENT AND FOLLOW-UP

The occurrence of an adverse event (AE) or serious adverse event (SAE) may come to the attention of study personnel during study visits and interviews of a study participant presenting for medical care, or upon review by a study monitor.

All AEs including local and systemic reactions not meeting the criteria for SAEs will be captured on the appropriate case report form (CRF). Information to be collected includes event description, time of onset, clinician's assessment of severity, relationship to study product (assessed only by those with the training and authority to make a diagnosis), and time of resolution/stabilization of the event. All AEs

occurring while on study must be documented appropriately regardless of relationship. All AEs will be followed to adequate resolution.

Any medical condition that is present at the time that the participant is screened will be considered as baseline and not reported as an AE. However, if the study participant's condition deteriorates at any time during the study, it will be recorded as an AE.

Changes in the severity of an AE will be documented to allow an assessment of the duration of the event at each level of severity to be performed. AEs characterized as intermittent require documentation of onset and duration of each episode.

The study monitor from the Ethics Committee of Peking University Third Hospital will record all reportable events with start dates occurring any time after informed consent is obtained until 7 (for non-serious AEs) or 30 days (for SAEs) after the last day of study participation. At each study visit, the investigator will inquire about the occurrence of AE/SAEs since the last visit. Events will be followed for outcome information until resolution or stabilization.

8.3.5 ADVERSE EVENT REPORTING

In case of AEs, the AEs should be reported in 24 hours to the study main sponsors and ethics committee by telephone or fax. And the AEs records should be submitted in 24 hours.

8.3.6 SERIOUS ADVERSE EVENT REPORTING

The study investigator shall complete an Unanticipated Adverse Device Effect Form and submit to the study sponsor and to the reviewing Institutional Review Board (IRB) as soon as possible, but in no event later than 10 working days after the investigator first learns of the effect. The study sponsor is responsible for conducting an evaluation of an unanticipated adverse device effect and shall report the results of such evaluation to the local medical administration ministry and to all reviewing IRBs and participating investigators within 10 working days after the sponsor first receives notice of the effect. Thereafter, the sponsor shall submit such additional reports concerning the effect as the local medical administration ministry requests.

8.3.7 REPORTING OF PREGNANCY

Pregnant patients will be excluded from the current trial.

8.4 UNANTICIPATED PROBLEMS

8.4.1 DEFINITION OF UNANTICIPATED PROBLEMS (UP)

The Office for Human Research Protections (OHRP) considers unanticipated problems involving risks to participants or others to include, in general, any incident, experience, or outcome that meets all of the following criteria:

- Unexpected in terms of nature, severity, or frequency given (a) the research procedures that are described in the protocol-related documents, such as the approved research protocol and informed consent document; and (b) the characteristics of the participant population being studied;
- Related or possibly related to participation in the research (“possibly related” means there is a reasonable possibility that the incident, experience, or outcome may have been caused by the procedures involved in the research).
- Suggests that the research places participants or others at a greater risk of harm (including physical, psychological, economic, or social harm) than was previously known or recognized.

8.4.2 UNANTICIPATED PROBLEM REPORTING

The investigator will report unanticipated problems (UPs) to the Ethics Committee of Peking University Third Hospital. The UP report will include the following information:

- Protocol identifying information: Protocol title and number, PI’s name, and the IRB project number;
- A detailed description of the event, incident, experience, or outcome;
- An explanation of the basis for determining that the event, incident, experience, or outcome represents an UP;
- A description of any changes to the protocol or other corrective actions that have been taken or are proposed in response to the UP.

To satisfy the requirement for prompt reporting, UPs will be reported using the following timeline:

- UPs that are serious adverse events (SAEs) will be reported to Ethics Committee of Peking University Third Hospital within 3 days of the investigator becoming aware of the event.
- Any other UP will be reported to the IRB and to Ethics Committee of Peking University Third Hospital within 10 of the investigator becoming aware of the problem.

9 STATISTICAL CONSIDERATIONS

9.1 STATISTICAL HYPOTHESES

- Primary Efficacy Endpoint(s):
The occurrence of POPF.
- Secondary Efficacy Endpoint(s):

Anastomosis time
Morbidity besides the POPF
Postoperative hospital stay

9.2 SAMPLE SIZE DETERMINATION

Sample size calculation is based on the primary endpoint: POPF rate. An assumed absolute risk of 10% difference in POPF occurrence is the appropriate basis for the calculation assuming 10% POPF in the SMMP technique group and 20% in the previous published data (Harnoss JC, Ulrich AB, Harnoss JM et al (2014) Use and results of consensus definitions in pancreatic surgery: a systematic review. *Surgery* 155:47-57). This calculation yields a total of 108 patients in the SMMP technique group, which assures a power of 80 % at a two-sided level of significance of 5 % (NCSS and PASS 11 (NCSS Statistical Software, Kaysville, UT, USA)). Assuming an expected withdrawal rate of 10 % during the trial, 12 additional patients will be included; therefore, the total sample size required is n = 120 patients.

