2.2 BACKGROUND

Pancreaticoduodenectomy (PD) is one of the most complicated surgical procedure and one of the standard treatments for benign and malignant disease of pancreatic head and periampullary region. Improvements in surgical techniques and the perioperative management of patients undergoing PD have reduced the surgical mortality rates to less than 3% in high-volume medical centers. However, the incidence of postoperative complication remains high, which ranges from 30% to 50% and the pancreatic fistula rate ranges from 5% to 40%.

Since the ISGPF classification was declared in 2005, it has been widely accepted. The rate of clinically relevant postoperative pancreatic fistula (CR-POPF) continued to persist at approximately 15%. The CR-POPF is one of the most important life-threatening complications that could lead to intra-abdominal abscess, hemorrhage, and sepsis. The exocrine output from the pancreatic remnant was now widely implicated as the initial cause of fistula. The underlying process is the continuous leakage of caustic proteases and lipolytic enzymes, with significant local consequences (abscess, pancreatic fistula, acute pancreatitis, pseudoaneurysm) and systemic sequelae (sepsis, shock, pulmonary insufficiency). So the clinically significant pancreatic fistula symptoms were caused by enzyme leakage and inflammation including bacterial and non-bacterial inflammation. The enzyme may be the initial promoting factor but the inflammation facilitated by enzyme was another important factor in the development of pancreatic fistula. The higher body weight, undilated main pancreatic duct and soft gland were widely accepted as the risk factors of CR-POPF and all these patient factor couldn't be changed by the surgeons. So the feasible and easy way to decrease the CR-POPF is to improve the enteric reconstruction technique of pancreatic stump.

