4 STUDY DESIGN

4.1 OVERALL DESIGN

This study is a prospective observational study evaluating the clinical efficacy of shark mouth modified pancreaticojejunostomy. The study will enroll a total of 120 participants who need to undergo the pancreaticoduodenectomy and will last for 2 years. The patients will undergo the shark mouth modified pancreaticojejunostomy procedure and be followed up. The primary endpoint of the study is the incidence of postoperative pancreatic fistula. The secondary endpoint is the postoperative hospital stay, morbidity, and the anastomosis time of the pancreaticojejunostomy procedure.

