5 STUDY POPULATION

5.1 INCLUSION CRITERIA

Patients who meet the following criteria will be included in the study:

1. Patients diagnosed with pancreatic cancer or other diseases which need pancreaticoduodenectomy
2. Operation-tolerated
3. Informed consent

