9.4.5 BASELINE DESCRIPTIVE STATISTICS

The baseline demographics information includes age, gender, and race. The baseline laboratory measurements include the blood routine test, serum liver function, serum renal function, serum amylase, serum tumor marker and coagulation function test.

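### The sample size sets a single SMMP group against a fixed 20% fistula rate that is not shown to fit the risk mix enrolled, so a crude rate below 20% cannot be credited to the technique

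*Protocol*

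**What the plan says.** Protocol section 4.1 describes the design: "This study is a prospective observational study evaluating the clinical efficacy of shark mouth modified pancreaticojejunostomy". All participants receive the procedure and there is no concurrent control.

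Section 9.2 bases the sample size on the postoperative pancreatic fistula (POPF) rate, "assuming 10% POPF in the SMMP technique group and 20% in the previous published data". The 20% is referenced to one paper, titled "Use and results of consensus definitions in pancreatic surgery: a systematic review". The section continues: "This calculation yields a total of 108 patients in the SMMP technique group". The power claimed for that number is 80%, with a two-sided test at the 5% level. Twelve patients are added for 10% withdrawal, which gives 120.

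The main entry criterion in section 5.1 is "Patients diagnosed with pancreatic cancer or other diseases which need pancreaticoduodenectomy". Patients must also be fit for operation and give consent. Section 5.2 excludes earlier abdominal surgery, pregnancy, an abandoned resection and withdrawal, and the synopsis limits age to 18 to 80 years. No criterion concerns duct size, gland texture or body weight.

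Section 2.2 states: "The higher body weight, undilated main pancreatic duct and soft gland were widely accepted as the risk factors of CR-POPF". It adds that surgeons cannot alter these factors, and it gives a published fistula range of 5% to 40%.

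On analysis, section 9.4.2 limits the primary endpoint to calculating the POPF incidence. Section 9.4.6 plans subgroups by age, sex, gland texture, main duct diameter and primary disease. The schedule of activities (section 1.3) records height, weight, texture, duct diameter and pathology.

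**The concern.** Sections 2.3.3 and 4.1 give clinical efficacy as the aim, and section 2.3.2 gives fewer fistulas as the expected benefit. With one group, any statement that fistulas became fewer needs an outside yardstick, and the only one the protocol uses for planning is the 20% in section 9.2.

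The distance from 20% has two components: what the anastomosis does, and how the enrolled patients' underlying fistula risk compares with that of the patients behind the 20%. The protocol itself names strong, unmodifiable risk factors, and both 10% and 20% lie well inside the range it cites. It gives no reason why 20% suits this cohort, and no step relates the observed rate to the rate these patients would be expected to have. A cohort with fewer soft glands or narrow ducts could produce the planned result with no benefit from SMMP. A cohort with more of them could hide a real benefit.

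**Working it through.** **Inputs from section 9.2.** Reference rate p0 = 0.20, rate under SMMP p1 = 0.10, two-sided 5% level (z = 1.960), power 80% (z = 0.8416), withdrawal 10%.

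**Step 1: reproduce the plan's figure.** For one proportion against a fixed value,

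n = [1.960·√(p0(1−p0)) + 0.8416·√(p1(1−p1))]² / (p0−p1)²

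= [1.960 × 0.4 + 0.8416 × 0.3]² / 0.01 = (0.7840 + 0.2525)² / 0.01 = 107.4, rounded up to 108.

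Then 108 / 0.90 = 120. Both stated figures reproduce. A comparison of two concurrent groups would need 199 per group, so 108 does treat the 20% as a known constant.

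**Step 2: what a result significantly below 20% means with 108 patients.** In the exact binomial test with 2.5% in the lower tail, the critical count is 13 events (13/108 = 12.0%). The probability of 13 or fewer is 2.1% if the true rate is 20%, and 81.0% if it is 10%, in line with the stated power.

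**Step 3: the same rule when SMMP has no effect but case mix sets the expected rate.** The protocol gives no case-mix data, so the rates below are assumptions shown as a range.

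| Expected rate from case mix alone | Probability of 13 or fewer events in 108 |
|---|---|
| 20% | 2.1% |
| 18% | 6.3% |
| 15% | 23.8% |
| 13% | 45.2% |
| 12% | 57.8% |
| 10% | 81.0% |

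In the other direction, at an expected rate of 25% the probability is below 0.1%.

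**Step 4: how large a shift in mix that takes.** Assume POPF of 30% in high-risk and 5% in low-risk glands, whatever the technique.

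- 60% high-risk: 0.6 × 30% + 0.4 × 5% = 20%
- 40% high-risk: 0.4 × 30% + 0.6 × 5% = 15%
- 20% high-risk: 0.2 × 30% + 0.8 × 5% = 10%

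Under these rates, moving from 60% to 40% high-risk raises the probability in step 2 from 2.1% to 23.8%, about elevenfold. Moving to 20% reproduces the whole planned difference.

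**Step 5: a confidence interval alone does not settle it.** With 11 events in 108 (10.2%) the exact 95% interval is 5.2% to 17.5%. It excludes 20%, but it reflects sampling error only and says nothing about whether 20% was the right comparator.

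**The case against.** The strongest reply is that the comparison is not a planned analysis. The 20% appears only in section 9.2, section 9.4.2 plans an incidence and nothing more, and section 9.4.3 disclaims inference, although it does so under the secondary endpoints. This stands. A reader might infer that the protocol prespecifies a confounded test against 20%, but it does not. What remains is that the size and power of the study are justified by that contrast, section 9.4.1 sets a P<0.05 threshold, and the aim is efficacy, so the result is likely to be read against 20%.

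A reader might also infer that the cohort's risk mix will go undescribed. That is not supported. The schedule records the risk factors, and section 9.4.6 would show both the size and the POPF rate of the texture, duct and disease strata. These subgroups supply no outside rate for each stratum, however, and body weight is missing from them. The baseline section, where "The baseline demographics information includes age, gender, and race", also lists laboratory values and omits the three risk factors. That is detail which a statistical analysis plan could supply, and texture and duct diameter are operative findings, so it is not counted here.

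It is also tempting to say that the populations are mismatched because the cited title refers to pancreatic surgery in general, or that any patient needing the operation may enter. A review with that title may still report rates for pancreaticoduodenectomy, and this cannot be checked from the protocol. Eligibility is restricted by fitness, age and earlier abdominal surgery, although none of these is a fistula-risk factor named in section 2.2. The defensible statement is that comparability is not shown.

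Finally, the magnitudes rest on assumed rates, nothing suggests that low-risk patients will be favoured, and section 2.2 does not attribute the 5% to 40% range to case mix. The risk factors there are stated for clinically relevant POPF, whereas the endpoint in section 9.4.2 includes grade A. These limits are fair. They bear on how large the problem will be, not on whether the crude rate can separate technique from mix.

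**Conclusion.** The point holds as a matter of interpretation. The sample size is arithmetically right, but its reference rate is not tied to the fistula risk of the patients enrolled, and the protocol's own background gives reasons to expect that rate to depend on them. A crude POPF rate below 20% would therefore not be evidence that SMMP lowers POPF.

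The size depends on an expected rate that the documents do not give. If case mix alone put it at 15%, the chance of a result significantly below 20% would be 24%; at 10% it would be 81%; at 20% it is 2.1%. These figures assume 108 evaluable patients, an exact test with 2.5% in the lower tail and no effect of SMMP. The direction of any imbalance is unknown. This is a worthwhile improvement at low cost, and it does not make the descriptive incidence itself invalid.

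**What to change.** 1. In sections 9.2 and 9.4.2, before analysis, choose a published reference for pancreaticoduodenectomy with rates by risk stratum, at least by gland texture and duct diameter, and with the same POPF definition as the endpoint. Report observed against expected POPF for the enrolled mix, beside the crude incidence with its confidence interval. The reference list already contains a risk-adjusted model, but its title refers to clinically relevant POPF, so it fits only an analysis limited to that outcome.
2. If no matching reference exists, state in section 9.4.2 that a crude difference from 20% will not be attributed to SMMP. This needs no outside data.
3. Add body weight or BMI to the subgroups in section 9.4.6. Height and weight are already collected.

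The cost is wording in three sections and a small analysis of data already planned for collection. There are two downsides. The expected rate is only as good as the published stratum rates behind it, and the result may look less favourable than a crude 10% against 20%.

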9.3 POPULATIONS FOR ANALYSES

- Modified Intention-to-Treat Analysis Dataset (e.g., participants who underwent the shark mouth modified pancreaticojejunostomy and have some particular amount of follow-up outcome data)
- Per-Protocol Analysis Dataset: defines a subset of the participants in the full analysis (ITT) set who complied with the protocol sufficiently to ensure that these data would be likely to represent the effects of study intervention according to the underlying scientific model (e.g., participants who took at least 80% of study intervention for 80% of the days within the maintenance period)
- Safety Analysis Dataset: defines the subset of participants for whom safety analyses will be conducted (e.g., participants who took at least one dose of study intervention)

9.4 STATISTICAL ANALYSES

9.4.1 GENERAL APPROACH

- For descriptive statistics. Categorical data will be presented in numbers with percentages. Continuous data will be presented in means with standard deviations or medians with ranges.
- A two-tailed P<0.05 was considered statistically significant.

9.4.2 ANALYSIS OF THE PRIMARY EFFICACY ENDPOINT(S)

POPF was defined and graded according to criteria proposed by the International Study Group on Pancreatic Fistula (ISGPF) as amylase-rich fluid (more than threefold greater than the upper limit of serum amylase level) of any measurable volume on or after postoperative day 3. POPF was subclassified into grade A (abnormal laboratory parameters without change in clinical management), grade B (abnormal laboratory parameters with non-invasive change in clinical management) and grade C (abnormal laboratory parameters requiring invasive treatment). In the present clinical trial, we will only calculate the incidence of POPF of the study participants.

Participants who underwent the shark mouth modified pancreaticojejunostomy and have some particular amount of follow-up outcome data (Modified Intention-to-Treat Analysis Dataset) will be analyzed.

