9.4.3 ANALYSIS OF THE SECONDARY ENDPOINT(S)

Anastomosis time is defined as time from beginning to end of shark mouth modified pancreaticojejunostomy, which is measured by the timer. Morbidities besides the POPF is classified according to the Clavien-Dindo definition as grade I to grade V. Postoperative hospital stay is defined as the length of hospital stay after the operation. As an observational study, no inferial analysis will be performed.

Participants who underwent the shark mouth modified pancreaticojejunostomy and have some particular amount of follow-up outcome data (Modified Intention-to-Treat Analysis Dataset) will be analyzed.

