10.1.2 STUDY DISCONTINUATION AND CLOSURE

This study may be temporarily suspended or prematurely terminated if there is sufficient reasonable cause. Written notification, documenting the reason for study suspension or termination, will be provided by the suspending or terminating party to study participants, investigator, and regulatory authorities>. If the study is prematurely terminated or suspended, the Principal Investigator (PI) will promptly inform study participants, the Ethics Committee of Peking University Third Hospital, and sponsor and will provide the reason(s) for the termination or suspension. Study participants will be contacted, as applicable, and be informed of changes to study visit schedule.

Circumstances that may warrant termination or suspension include, but are not limited to:

- Determination of unexpected, significant, or unacceptable risk to participants
- Demonstration of efficacy that would warrant stopping
- Insufficient compliance to protocol requirements
- Data that are not sufficiently complete and/or evaluable
- Determination that the primary endpoint has been met
- Determination of futility

Study may resume once concerns about safety, protocol compliance, and data quality are addressed, and satisfy the sponsor, IRB and/or the local medical administration ministry.

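### The sample size rests on a two-sided 5% test of POPF against 20%, but the protocol states no such hypothesis and limits the primary analysis to calculating an incidence

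*Protocol*

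**What the plan says.** - **Section 9.2** bases the calculation on the primary endpoint ("Sample size calculation is based on the primary endpoint: POPF rate"). It assumes 10% with the new technique and 20% from published data, and arrives at 108 patients, "which assures a power of 80 % at a two-sided level of significance of 5" per cent. Twelve more are added for 10% withdrawal, giving 120.
- **Section 9.1**, whose heading promises hypotheses, gives for the primary endpoint only "The occurrence of POPF". It has no null, no alternative and no reference rate.
- **Section 9.4.1** has a general line, "A two-tailed P<0.05 was considered statistically significant", with no test, endpoint or comparator attached.
- **Section 9.4.2**, on the primary endpoint, defines and grades POPF and then says "In the present clinical trial, we will only calculate the incidence of POPF of the study participants".
- **Section 9.4.3**, on the secondary endpoints, adds "As an observational study, no inferial analysis will be performed".
- **Section 4.1** sets the frame: "This study is a prospective observational study evaluating the clinical efficacy of shark mouth modified pancreaticojejunostomy".
- **Section 10.1.2** lists among the grounds for ending the study "Determination that the primary endpoint has been met", and also futility.

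**The concern.** Power and significance level are properties of a decision rule. Section 9.2 claims both, but neither 9.1 nor 9.4 contains a rule to which they could apply. The 20% figure appears only in 9.2, and nothing in the planned analysis compares the result with it.

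The protocol thus gives two answers to whether the primary analysis is a confirmatory comparison with 20% or a description. An unseen SAP could supply the name of the test. It could not consistently add a comparison that the protocol's own primary-analysis section leaves out by promising only an incidence.

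At stake is the reading of the main result. The trial will report a rate, and the 20% is on record beside it. Whether a rate somewhat under 20% counts as success would be decided after the data are seen.

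**Working it through.** **Inputs (section 9.2).** Reference rate p0 = 0.20, treated as fixed; assumed rate p1 = 0.10; two-sided alpha 0.05 (z = 1.960); power 80% (z = 0.8416); withdrawal 10%. One arm (section 4.1).

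**1. Reproduce the plan's figure.** One-sample test of a proportion, normal approximation:

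n = [1.960·√(0.20·0.80) + 0.8416·√(0.10·0.90)]² / (0.10)² = (0.7840 + 0.2525)² / 0.01 = 107.43, so 108.

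108 / 0.9 = 120. Both stated figures are correct. Other forms do not give 108: one-sided 83, arcsine 98, continuity-corrected 118, two equal arms 199 per arm. The stated N therefore identifies the intended analysis as a two-sided one-sample test against a fixed 20%.

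**2. What a bare rate would show.** Suppose the true rate is 20% and X is the number of patients with POPF.

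- n=108: 20% is 21.6 patients, so below 20% means X ≤ 21; probability 0.5001.
- n=120: 20% is 24 patients, so below 20% means X ≤ 23; probability 0.4636.
- Over analysed n of 108 to 120 the range is 0.462 (n=110) to 0.538 (n=111).

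**3. What a rule matching section 9.2 would show.** Rule: the exact (Clopper-Pearson) 95% upper limit is below 20%. For n = 108 to 120 this is the same as P(X ≤ x | 0.20) < 0.025.

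| Analysed n | Largest x meeting the rule | P(rule met), true 20% | Power, true 10% | Miss, true 10% |
|---|---|---|---|---|
| 108 | 13 (12.0%; CI 6.6%–19.7%) | 0.0210 | 0.8101 | 0.1899 |
| 112 | 13 | 0.0137 | 0.7718 | 0.2282 |
| 119 | 15 | 0.0241 | 0.8632 | 0.1368 |
| 120 | 15 (12.5%; CI 7.2%–19.8%) | 0.0218 | 0.8560 | 0.1440 |

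The cut-off is 13 for n = 108–112, 14 for 113–118 and 15 for 119–120. The rows for 112 and 119 are the lowest and highest power in that range.

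**4. The results open to dispute.** Counts below 20% that do not exclude it are 14–21 of 108 and 16–23 of 120. If the true rate is 10%, these bands have probability 0.1890 and 0.1432.

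**5. Does the form of the test matter?** The normal-approximation test behind 9.2 rejects downward when the rate is below 0.20 − 1.96·√(0.16/n). At n=108 this is 0.1246, or 13.45 patients, so 13. At n=120 it is 0.1284, or 15.41 patients, so 15. These cut-offs equal the exact ones.

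**The case against.** - **The error rate in step 2 belongs to a rule nobody wrote.** Followed literally, the trial makes no claim about 20%, so it has no false-claim rate. This is fair: the 46%–54% shows how little a bare rate would support such a claim, not an error rate of the protocol. But then the 80% power in 9.2 has no function.
- **Little is left open, because 9.2 fixes the benchmark, level and sidedness.** If a test is made, this is largely right. Over n = 108–120, the interval rule and a minimum-likelihood exact p-value disagree only at n = 112, 118 and 119, each time by one event. What remains open is whether a test is made at all.
- **The word only in 9.4.2 may mean overall rather than by-grade incidence.** That is possible. On that reading, too, no section compares the incidence with 20%.
- **The P<0.05 line may serve the subgroup analyses in 9.4.6.** It may. In that case it does not supply the missing primary test either.
- **The grounds for ending the study in 10.1.2 look like generic template text.** The document does contain unedited template passages, so this section is supporting evidence only. The same goes for 9.4.3, which concerns secondary endpoints, and for the word observational in 4.1.
- **The harm is recoverable.** Counts and percentages will be reported, so any reader can compute an interval. True, but a criterion applied after the result is known does not carry the stated power and level.

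**Conclusion.** The concern holds. The arithmetic of 9.2 is right; the defect is that its test appears nowhere in 9.1 or 9.4, and 9.4.2 as written leaves it out. This is a contradiction within the protocol on the primary endpoint, not a detail deferred to a SAP.

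Its size is the gap between the two readings. With a true rate of 20%, a rate merely below 20% occurs about half the time; the interval rule is met 1.4%–2.4% of the time over n = 108–120. These figures assume that 20% is a fixed reference, that patients are independent and that 108 to 120 are analysed. The power figures also assume a true rate of 10%.

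**What to change.** Bring 9.1, 9.2, 9.4.1 and 9.4.2 into agreement in one of two ways. N stays at 120 under both.

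**(a) Confirmatory.**
- In 9.1, state H0: POPF rate = 20%; H1: POPF rate differs from 20%.
- In 9.4.2, replace the sentence limiting the analysis to incidence with: *The POPF rate will be reported with its exact (Clopper-Pearson) 95% CI; a rate below 20% is claimed only if the upper limit is below 20% at the analysed n (13 or fewer of 108; 15 or fewer of 120).*
- In 9.4.1, say that the two-sided 5% level applies to the primary endpoint through this rule, and whether it is meant for anything else, such as the subgroups.
- Do not add a separate minimum-likelihood exact p-value, because it can contradict the interval: 14/112 gives p = 0.045 with upper limit 20.08%, 15/118 gives 0.04998 with 20.10%, and 15/119 gives 0.0504 with 19.94%.
- State that this is a comparison with a fixed historical figure, not a controlled comparison.

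**(b) Descriptive.** Delete the power and significance claim from 9.2, and the P<0.05 line as far as it concerns the primary endpoint. Justify N by precision: 11/108 (10.2%) has an exact 95% CI of 5.2%–17.5%, and 12/120 (10.0%) has 5.3%–16.8%.

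Under either option, reconcile the wording in 10.1.2 on the primary endpoint being met and on futility with the choice made.

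**Cost.** Protocol wording only; no extra patients, visits or data. Under (a) the trial can miss its criterion even if the true rate is 10%: 19.0% at n=108, 14.4% at n=120, and 22.8% at n=112, where power is lowest. Under (b) the power claim is given up.
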